## 8 DOSE DELAYS/DOSE MODIFICATIONS

### 8.1 Radiotherapy Dosing

Radiotherapy for this trial may take place over a maximum of 10 business days before it is considered a protocol deviation. There are no dose adjustments (reductions, omissions) associated with radiotherapy.

## 8.2 Chemotherapy Dosing

FOLFOX				
Chemotherapy	Starting Dose	Dose Level -1	Dose Level -2	Dose Level -3
Oxaliplatin	85 mg/m 	65 mg/m 	50 mg/m 	40 mg/m 
Bolus 5-FU	400 mg/m 	300 mg/m 	200 mg/m 	100 mg/m 
Infusion 5-FU	2400 mg/m 	1920 mg/m 	1600 mg/m 	1360 mg/m 
Leucovorin	400 mg/m 	400 mg/m 	400 mg/m 	400 mg/m 

CAPOX				
Chemotherapy	Starting Dose	Dose Level -1	Dose Level -2	Dose Level -3
Oxaliplatin	130 mg/m 	100 mg/m 	80 mg/m 	50 mg/m 
Capecitabine	1000 mg/m  BID	800 mg/m  BID	650 mg/m  BID	500 mg/m  BID

Dose modifications of the chemotherapy agents may be made independently of each other. Patients unable to tolerate one of more drugs due to toxicity may remain on study with the other drugs. All toxicities should be graded according to the Common Terminology Criteria for Adverse Events (CTCAE), version 4.0. Dose modifications are based upon dose level administered at last treatment day. If the dose level has been reduced due to toxicity, re-escalation is permitted at the discretion of the primary treating physician.

## 8.3 Dose Modifications for Toxicity Related to FOLFOX-6

Dose modifications during FOLFOX chemotherapy are at the discretion of the primary treating provider. The use of 5-FU bolus is at the discretion of the treating physician. Modifications should be reported to research coordinator. Refer to the tables below for guidance regarding suggested dose reductions and treatment delays, consistent with best oncologic practices.

Toxicity NCI Grade (Value)	Worst interval toxicity	Day of treatment	
Neutropenia (ANC)			
Grade 1 (ANC < LLN – 1500/mm  )	Maintain dose level	If ANC < 1000 on day of treatment, hold and check weekly until $\geq$ 1000 mm  . Then treat based on interval toxicity. If ANC < 1000 after 4 weeks, discontinue therapy.	
Grade 2 (ANC < 1499 – 1000/mm  )			
Grade 3 (ANC < 999 – 500/mm  )			
Grade 4 (ANC < 500/mm  )	Reduce 1 dose level		
Thrombocytopenia			
Grade 1 (PLT < LLN – 75,000/mm  )		If PLT < 75,000 on day of treatment, hold and check weekly until $\geq$ 75,000 mm  . Then treat based on interval toxicity. If PLT < 75,000 after 4 weeks, discontinue therapy.	
Grade 2 (PLT 74,999 – 50,000/mm  )			
Grade 3 (PLT 49,999 – 25,000/mm  )			

Grade 4 (PLT< 25,000/mm  )		
Diarrhea		
Grade 1	Maintain dose level	
Grade 2	Reduce 5-FU and oxaliplatin 1 dose level	
Grade 3		
Grade 4		Hold chemotherapy if any grade of diarrhea above grade 1 is present with the patient not taking antidiarrheal agents within 24 hours of treatment. Reduce 5-FU and oxaliplatin 1 dose level upon resolution of diarrhea. If diarrhea has not resolved within 4 weeks of scheduled treatment day, discontinue therapy.
Other nonhematologic toxicities (except neurologic, alopecia, anorexia, nausea/vomiting if can be controlled by antiemetics)		
Grade 1	Maintain dose level	Maintain dose level
Grade 2		
Grade 3	Reduce 1 dose level	Hold until resolved to grade $\leq 1$ . Reduce 5-FU and oxaliplatin 1 dose level
Grade 4		

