### **Recommended Dose Modification and Toxicity Management Guidelines for Diarrhea Attributable to Capecitabine**

Toxicity Grades	During a Course of Therapy	Dose Adjustment for Next Treatment (% of starting dose)
Grade 1	Maintain dose level	Maintain dose level
Grade 2		
-1st appearance	Interrupt until resolved to grade 0-1	100%
-2nd appearance		75%
-3rd appearance		50%
-4th appearance	Discontinue treatment permanently	-
Grade 3		
-1st appearance	Interrupt until resolved to grade 0-1	75%
-2nd appearance		50%
-3rd appearance	Discontinue treatment permanently	-
Grade 4		
-1st appearance	Discontinue permanently OR If physician deems it to be in the patient's best interest to continue, interrupt until resolved to grade 0-1	50%

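### Minor wording error in discretionary guidance: read literally, the FOLFOX day-of-treatment diarrhea hold in section 8.3 does not apply to a patient who is taking antidiarrheals

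*Combined protocol and SAP*

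**What the plan says.** The FOLFOX table in section 8.3 treats diarrhea in two columns.

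- **Worst interval toxicity.** From grade 2 the suggestion is "Reduce 5-FU and oxaliplatin 1 dose level". It is printed at grade 2, and the grade 3 and 4 cells are blank in the extracted text. It carries no antidiarrheal condition.
- **Day of treatment.** The hold reads "Hold chemotherapy if any grade of diarrhea above grade 1 is present with the patient not taking antidiarrheal agents within 24 hours of treatment". Two sentences follow: "Reduce 5-FU and oxaliplatin 1 dose level upon resolution of diarrhea", and "If diarrhea has not resolved within 4 weeks of scheduled treatment day, discontinue therapy". Neither mentions antidiarrheals.

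The same section sets the status of the table: "Dose modifications during FOLFOX chemotherapy are at the discretion of the primary treating provider", and "Refer to the tables below for guidance regarding suggested dose reductions and treatment delays, consistent with best oncologic practices". Section 12 adds that both regimens are given to standard-of-care guidelines.

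For the other regimen, section 8.5 recommends antidiarrheals, and its capecitabine diarrhea table says "Interrupt until resolved to grade 0-1" for grades 2 and 3. For grade 4 it says to discontinue, or: "If physician deems it to be in the patient's best interest to continue, interrupt until resolved to grade 0-1".

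**The concern.** The word 'with' joins the antidiarrheal phrase to the trigger for the hold. A patient with grade 3 diarrhea who has taken nothing meets the trigger. A patient with grade 3 diarrhea despite loperamide or a similar agent does not. The second patient has the more refractory toxicity, so the rule runs backwards for that case.

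The situation is realistic. Under section 7.1 FOLFOX starts 2 to 4 weeks after the end of pelvic radiotherapy, and antidiarrheals are ordinary supportive care. What is at stake is whether a safety suggestion used at several sites says what it should for these patients. No statistical quantity depends on it.

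**Working it through.** The plan gives no figure to reproduce. The check is a logical reading of the rule and a search for any other text that would close the gap.

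**1. The literal rule.** Hold if (grade above 1) AND (no antidiarrheal within 24 hours). Crossing three grades with antidiarrheal use gives 3 × 2 = 6 combinations.

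| Diarrhea on the day | Antidiarrheal within 24 h | Hold, current wording | Hold, if grade alone decides |
|---|---|---|---|
| Grade 2 | no | yes | yes |
| Grade 2 | yes | no | yes |
| Grade 3 | no | yes | yes |
| Grade 3 | yes | no | yes |
| Grade 4 | no | yes | yes |
| Grade 4 | yes | no | yes |

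The current wording holds in 3 of 6; a rule on grade alone holds in 6 of 6. These counts describe the scope of the wording, not how often patients fall in each row.

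**2. Does other FOLFOX text supply the hold?**

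- The grade 3-4 hold lower in the same table belongs to the row for *other* nonhematologic toxicities. Diarrhea has its own row, so that hold does not literally reach it.
- The interval-toxicity column sets a dose level. It neither holds treatment nor clears the patient for it.
- The 4-week sentence sets an outer limit for discontinuation. It is not a same-day hold.
- Sections 7.1, 7.2, 8.2 and 8.4 contain no diarrhea hold.

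**3. How does the protocol handle comparable cases?**

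- The neutropenia and thrombocytopenia holds in 8.3 depend only on the count that day.
- Nausea and vomiting are excepted in 8.3 only where antiemetics can control them. There the supportive drug matters because it works. In the diarrhea cell, merely taking the drug removes the hold while the toxicity is still present.
- The capecitabine table has 4 grade 2 entries (3 interrupt, 1 discontinue), 3 grade 3 entries (2 interrupt, 1 discontinue) and 1 grade 4 entry (discontinue or interrupt). That is 4 + 3 + 1 = 8 entries. All 8 stop the drug, and none depends on antidiarrheal use. This count reads the interrupt cells as covering the blank rows below them.

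**4. The restart standard.** The diarrhea row says 'resolution' without a grade. The row for other nonhematologic toxicities uses grade 1 or lower, and the capecitabine table uses grade 0-1. A requirement to be free of antidiarrheals for 24 hours makes sense as a condition for restarting. Attached to the hold trigger, it produces the gap in step 1.

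**The case against.** The strongest reply is that the phrase can be read as setting how diarrhea is assessed: the patient should be at grade 1 or lower without antidiarrheal support. On that reading, diarrhea above grade 1 despite antidiarrheals fails all the more clearly. The two sentences after the hold also point to waiting for resolution. This is probably what the authors meant. It supports a wording error rather than an unsafe policy, but the sentence still does not say it.

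A reader might go further and infer that the table directs a reduced dose on that day. For example, oxaliplatin at level -1 is 65/85 = 76% of the starting dose in section 8.2. The documents do not support this. No sentence says to give chemotherapy during active grade 2-4 diarrhea; the interval column only sets a level; the day-of-treatment cell places the reduction after resolution; and applying the reduction to grades 3-4 assumes a merged cell broken in extraction. The gap in the hold does not depend on that cell, because the hold states its own grade range.

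Two further points stand. The table is discretionary, section 5.2 has a medical oncology physician or nurse assess the patient at each cycle, and section 12 invokes standard of care, so a careful clinician would hold anyway. And the capecitabine table governs interruption of a daily oral drug, so it is a comparison and not the same decision.

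**Conclusion.** The concern holds as a minor wording error. Taken literally, the suggested FOLFOX hold leaves out grade 2-4 diarrhea that persists on antidiarrheals, and no other FOLFOX text supplies a hold. The practical effect is likely small, given provider discretion and standard-of-care administration.

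The size cannot be put as a frequency: the documents give no diarrhea rate and no split between FOLFOX and CAPOX. A reader might also infer an effect on the toxicity endpoints or on clinical complete response. Nothing in the documents supports one, and sample size, error rates and the primary analysis are untouched.

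The conclusion rests on the plain two-condition reading of the sentence. That the 24-hour phrase was meant as a restart condition is an inference from the rest of the cell, and the investigators need to confirm it.

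**What to change.** Replace the day-of-treatment diarrhea text in the 8.3 table with:

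*Hold chemotherapy if diarrhea above grade 1 is present on the day of treatment, whether or not the patient is taking antidiarrheal agents. Resume, with 5-FU and oxaliplatin reduced 1 dose level, when diarrhea is grade 1 or lower without antidiarrheal agents for 24 hours.*

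Measure the 4-week discontinuation limit against that same restart standard, and keep provider discretion. Ask the investigators to confirm that the 24-hour phrase was intended as the restart condition. If it was not, delete it from the second sentence; the first sentence stands either way.

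The cost is one table cell in an amendment. Some FOLFOX cycles may be delayed, and those delays may count toward the 4-week total in section 7.1, beyond which the case goes to the Principal Investigator. With the 24-hour condition, a held patient whose diarrhea is controlled only on antidiarrheals stays on hold and could reach the discontinuation limit, which is a further reason to confirm intent. The benefit is confined to FOLFOX patients still to be treated; the documents do not state accrual status.

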#### **8.4 Dose Modifications for Neurologic Toxicity (Paresthesia or Dysesthesia) Related to Oxaliplatin**

Grade	Duration of Toxicity		
	1 – 7 Days	> 7 Days	Persistent Between Doses
Grade 1 Short duration that resolves and does not interfere with function	No change	No change	No change
Grade 2 Interfering with function, but not activities of daily living (ADL)	No change	No change	Reduce oxaliplatin 1 dose level
Grade 3 With pain or with functional impairment that also interferes with ADL	1 st time: reduce oxaliplatin 1 dose level  2 nd time: reduce oxaliplatin another dose level	1 st time: reduce oxaliplatin 1 dose level  2 nd time: reduce oxaliplatin another dose level	Discontinue oxaliplatin
Grade 4 Persistent symptoms that are disabling or life-threatening	Discontinue oxaliplatin	Discontinue oxaliplatin	Discontinue oxaliplatin

#### **8.5 Dose Modifications for Toxicity Related to CAPOX**

Dose modifications may be made as per standard of care following the package inserts or standard practice. Based on recent report by Cercek et al., in Lancet Oncology 2018 (PMID29566109), dose modification of 5-FU or oxaliplatin is quite common, up to 54% with oxaliplatin and 25% with 5-FU. However, about 85% were able to complete >75% of

planned doses. Therefore, we believe up to 70% of patients requiring dose modification would be acceptable.

Specifically, for diarrhea, the following table is recommended for dose modification of capecitabine. Standard antidiarrheal agents will be recommended.

### **Recommended Dose Modification and Toxicity Management Guidelines for Diarrhea Attributable to Capecitabine**

Toxicity Grades	During a Course of Therapy	Dose Adjustment for Next Treatment (% of starting dose)
Grade 1	Maintain dose level	Maintain dose level
Grade 2		
-1st appearance	Interrupt until resolved to grade 0-1	100%
-2nd appearance		75%
-3rd appearance		50%
-4th appearance	Discontinue treatment permanently	-
Grade 3		
-1st appearance	Interrupt until resolved to grade 0-1	75%
-2nd appearance		50%
-3rd appearance	Discontinue treatment permanently	-
Grade 4		
-1st appearance	Discontinue permanently OR If physician deems it to be in the patient's best interest to continue, interrupt until resolved to grade 0-1	50%

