## **12 PHARMACEUTICAL INFORMATION**

FOLFOX and CAPOX are standard of care, FDA-approved regimen for the treatment of rectal cancer, and treatment will be provided and administered according to standard of care guidelines. More detailed information can be found in the products' package inserts.

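### The recommended capecitabine diarrhea table in Section 8.5 sets the next dose from the starting dose with no cap at the dose last given, so as printed it can raise the dose in a patient already reduced

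*Combined protocol and SAP*

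**What the plan says.** Section 8.2 lists four capecitabine dose levels: a starting dose of 1000 mg/m2 BID, then 800, 650 and 500. Below the FOLFOX and CAPOX level tables it states: "Dose modifications are based upon dose level administered at last treatment day". For a patient reduced because of toxicity, it adds that "re-escalation is permitted at the discretion of the primary treating physician". It also lets each agent be modified separately, so capecitabine may already have been lowered for another toxicity when diarrhea first appears.

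Section 8.5 opens with latitude for CAPOX: "Dose modifications may be made as per standard of care following the package inserts or standard practice". For diarrhea it then becomes specific: "the following table is recommended for dose modification of capecitabine". The right-hand column of that table is headed "Dose Adjustment for Next Treatment (% of starting dose". Its entries are:

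- Grade 1: "Maintain dose level".
- Grade 2: 100%, 75% and 50% at the first, second and third appearance, then permanent discontinuation.
- Grade 3: 75% and 50% at the first and second appearance, then permanent discontinuation.
- Grade 4, first appearance: "Discontinue permanently OR If physician deems it" to be in the patient's interest to continue, in which case 50%.

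Section 12 says of both regimens that "treatment will be provided and administered according to standard of care guidelines".

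**The concern.** One section works from the dose last given and the other from the starting dose. For a patient still at 1000 the two coincide. For a reduced patient they do not, and the table has no ceiling at the current dose.

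The table's own rows show the anomaly. The grade 1 row holds the current dose, so a patient at 650 stays at 650. The next row, for a first grade 2, prints 100% of the starting dose, which is 1000. The milder episode holds the dose and the worse one raises it, in the drug to which the diarrhea is attributed.

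At stake is dosing consistency and safety for CAPOX patients across several institutions. A site that follows the printed percentage and a site that works from the last dose would treat the same reduced patient differently.

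**Working it through.** The plan gives no figure of its own to reproduce here. The check is dose arithmetic.

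**Inputs.** Dose levels 1000, 800, 650 and 500 mg/m2 BID (Section 8.2, where 1000 is labelled the starting dose). Table percentages from Section 8.5, as listed above.

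**Formula.** Next dose as printed = listed percentage × 1000. Relative change = next dose ÷ current dose − 1.

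**Step 1: patient already reduced for another toxicity, first diarrhea episode.** This case does not depend on how appearances are counted.

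| Current dose | First grade 2 (100% → 1000) | First grade 3 (75% → 750) | First grade 4, if continued (50% → 500) |
|---|---|---|---|
| 800 | 1000/800 = 1.25, +25% | 750/800 = 0.94, −6% | falls |
| 650 | 1000/650 = 1.538, +54% | 750/650 = 1.154, +15% | falls |
| 500 | 1000/500 = 2.00, +100% | 750/500 = 1.50, +50% | unchanged |

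For grades 2 and 3, five of the six cells are increases. Grade 4 never raises the dose.

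**Step 2: diarrhea alone, starting at full dose.** No single episode raises a dose of 1000, but a second episode can raise a dose that the table itself has lowered. The result depends on whether appearances are counted per grade or across grades, which the table does not say. Only pairs with a listed percentage at both episodes are counted.

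- Per grade: eight ordered pairs of grades 2, 3 and 4 (all except 4 then 4). Three rise: grade 3 then 2 (750 → 1000), grade 4 then 2 (500 → 1000), grade 4 then 3 (500 → 750).
- Across grades: six pairs, because a second episode of grade 4 has no entry. One rises: grade 4 then 2 (500 → 750).

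The pairs that begin with grade 4 arise only if the physician chose to continue, since discontinuation is the other option.

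**Step 3: effect of a cap.** Next dose = min(listed percentage × 1000, last dose). By construction this cannot exceed the last dose, so the five increases in Step 1 become none, and those in Step 2 become none under either counting rule.

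**Step 4: what the cap leaves open.** For a first grade 3 at 800, the cap gives min(750, 800) = 750. Applying 75% to the last dose would give 0.75 × 800 = 600. The two bases still differ when the dose falls. For a first grade 3 at 650, the cap gives min(750, 650) = 650, and at 500 it gives 500, so by itself it holds the dose and does not step it down.

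These are counts of table cells, not frequencies. The documents do not allow an estimate of how often such patients would occur.

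**The case against.** The strongest reply is that the table compels nothing. It is a recommendation, Section 8.5 allows package inserts and standard practice, and Section 12 points to standard of care. Moving a patient from 650 to 1000 is a re-escalation, which Section 8.2 leaves to the physician, and a sensible clinician would not choose it right after new diarrhea. The extreme cells are also remote. CAPOX runs for five cycles; if reductions go one level per cycle (an assumption), 500 is first reached in cycle 4, so a rise from 500 to 1000 could affect only cycle 5.

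Most of this stands and sets the weight of the point. It does not remove the printed increase. Discretionary re-escalation is a clinical choice, whereas here the increase is the listed response to a new toxicity. The documents do not show whether the outside sources contain a cap.

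A reader might also infer that Sections 8.2 and 8.5 prescribe two competing doses for the same patient. The documents do not support that. Section 8.2 gives levels and a reference basis but no next dose for capecitabine diarrhea, and the one-level reductions for diarrhea are in Section 8.3, which covers FOLFOX. What is missing is a statement reconciling two bases. Nor does the more specific wording of Section 8.5 settle which basis governs: that the table overrides Section 8.2 is an inference, and it is the reading that produces the increases.

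**Conclusion.** The point holds as a minor drafting defect. As printed, the table raises the dose after a first grade 2 diarrhea at every reduced level, and after a first grade 3 at 650 or 500, with increases from 15% to 100%. It can also raise the dose within diarrhea alone, in a number of sequences that depends on an unstated counting rule.

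This rests on two assumptions: the patient began at 1000, and the column heading is read literally against that dose. If Section 8.2 is taken to govern, no increase follows except by the physician's choice.

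A reader might infer that the protocol directs physicians to escalate, or that the trial's results are in doubt. Neither follows. The table is advisory, and no endpoint, sample size or error rate is affected.

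**What to change.** Add to the Section 8.5 diarrhea table: *The next dose must not exceed the last dose given: use the lower of the listed percentage of the starting dose and the last dose. Further reduction, by a Section 8.2 dose level, remains at the physician's discretion.*

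The first sentence removes the unintended increases. The second keeps the cap from being read as a ruling against stepping down: a patient at 650 with a first grade 3 could go to 500. At 500 there is no lower Section 8.2 level to use. Later discretionary re-escalation under Section 8.2 is unchanged. The change does not make the starting-dose and last-dose bases agree in other respects, and should not be described as doing so.

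The cost is two sentences in the next amendment, with no effect on sample size, visits or analysis.

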## **9 MR IMAGING GUIDELINES**

### **9.1 Requirements**

- **Imaging must be performed with at least 1.5 T (3 T also acceptable).**
- External phased array coils must be used
- Endorectal coils must not be used
- 2D fast T2-weighted sequences in the sagittal, axial and coronal planes must be obtained.
- Axial sequence angled perpendicular to the tumor and a coronal sequence angled parallel to the tumor for accurate staging
- DWI sequences should be obtained
- Contrast agents may be used (should contrast agents be used, imaging without contrast must also be obtained)

## **10 ADVERSE EVENT REPORTING**

The entities providing oversight of safety and compliance with the protocol require reporting as outlined below. Please refer to Appendix C for definitions and Appendix D for a grid of reporting

timelines.

Adverse events will be tracked from start of treatment through one year after the start of radiation therapy. All adverse events must be recorded on the toxicity tracking case report form (CRF) with the exception of:

- Baseline adverse events, which shall be recorded on the medical history CRF
- Grade 1 or grade 2 events, which will not be captured or reported

Refer to the data submission schedule in Section 14 for instructions on the collection of AEs in the EDC.

Reporting requirements for Washington University study team may be found in Section 10.1. Reporting requirements for secondary site study teams participating in Washington University-coordinated research may be found in Section 10.2.

Please note that toxicities will be collected using version 4.0 of the CTCAE for comparison to a previous study in this population, HRPO# 201512140.

